8.2.2. Prohibited Medications and Dietary Supplement

Use of any of the following drugs either in mono or combination therapy within 5 weeks prior to Visit S1 (unless otherwise stated) or a plan to use these drugs during the study is **prohibited**:

- Systemic corticosteroids. Topical and inhaled corticosteroids are allowed;
- Simvastatin ≥ 40 mg/day;
- Select non-statin LDL-C-modifying therapies:
 - Fibrates including gemfibrozil (Lopid®), fenofibrate (Antara®, Lofibra®, Tricor®, and Triglide™, Lipantil®, Supralip®), clofibrate (Atromid-S), ciprofibrate (Modalim®), bezafibrate (Bezalip®);
 - Niacin and derivatives including Niaspan® Rx and over-the-counter niacin (crystalline > 500 mg/day or slow release or timed release at any dose);
 - Bile acid sequestrants including Cholestyramine (Questran®, Questran® Light, Prevalite®, Locholest®, Locholest® Light); colestipol (Colestid®); colesevelam HCl (WelChol®, Cholestagel®);
 - Ezetimibe (Zetia®, Ezetrol®) other than that which is study-supplied;
 - Mipomersen or lomitapide (6 months prior to screening);
 - Apheresis;
 - PCSK9 inhibitors (4 months prior to screening except PCSK9 siRNA, which are prohibited if used at any time in the past);
 - CETP inhibitors (12 months prior to screening);
 - Red yeast rice extract-containing products (2 weeks prior to screening).

Other Drugs:

- Probenecid or cyclosporine;
- Potent CYP3A4 inhibitors including amiodarone, azoles (fluconazole, itraconazole, ketoconazole, posaconazole, voriconazole), bosentan, clarithromycin, cobicistat, conivaptan, danazol, daptomycin, diltiazem, domperidone, erlotinib, erythromycin, fusidic acid, mibepradil, nefazodone, piperaquine, protease inhibitors (atazanavir, boceprevir, darunavir, delavirdine, fosamprenavir, indinavir, lopinavir, nelfinavir, ritonavir, saquinavir, telaprevir, tipranavir), quinupristin/dalfopristin, telithromycin, verapamil.

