Other than statins, only a few drugs are approved to lower LDL-C. Although LDL-C lowering is robust with proprotein convertase subtilisin kexin type 9 (PCSK9) inhibitors, use of these drugs is limited by mode of administration and other accessibility issues. The oral drug EZE, an intestinal cholesterol absorption inhibitor, lowers LDL-C by 18% in patients with primary hyperlipidemia ([Knopp 2003](#)). Other oral LDL-C-lowering therapies include coleselam, a bile acid sequestrant that lowers LDL-C by up to 18% but is limited by gastrointestinal side effects ([Insull 2001](#)), while extended-release niacin in doses up to 2 g lowers LDL-C by up to 17% ([Goldberg 1998](#)). Finally, fenofibrate, an activator of peroxisome proliferator-activated receptor alpha, lowers LDL-C by approximately 20% in patients with hypercholesterolemia ([Knopp 1987](#)), but may substantially increase LDL-C in patients with hypertriglyceridemia.

An increasing body of evidence suggests that the absolute amount of LDL-C lowering is proportional to CVD risk reduction in statin and nonstatin therapies that lower LDL-C via upregulation of LDL receptors. Bempedoic acid and EZE are oral therapies that work by divergent mechanisms to lower LDL-C via up-regulation of LDL receptors. The magnitude of LDL-C lowering that can be achieved by concurrent administration of these oral therapies on a background of maximally tolerated statin therapy is unknown.

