16. Previous enrollment in a BA clinical study;
17. Use of any of the following drugs within 5 weeks prior to screening (Visit S1) unless otherwise stated or a plan to use these drugs during the study is **prohibited**:
 - Systemic corticosteroids. Topical and inhaled corticosteroids are allowed.
 - Simvastatin ≥ 40 mg/day;
 - Non-statin LDL-C-modifying therapies:
 - Fibrates (including fenofibrate);
 - Niacin and derivatives;
 - Bile acid sequestrants;
 - Ezetimibe;
 - Mipomersen or lomitapide (6 months prior to screening);
 - Apheresis;
 - PCSK9 inhibitors (4 months prior to screening except PCSK9 small interfering RNA (siRNA), which are prohibited if used at any time in the past);
 - Cholesteryl ester transfer protein (CETP) inhibitors (12 months prior to screening);
 - Red yeast rice extract-containing products (2 weeks prior to screening);
18. Starting or adjusting the dose of the following permitted drugs within 5 weeks prior to screening. These drugs are **allowed as long as stable** at least 5 weeks prior to screening (Visit S1) unless otherwise noted:
 - Hormone replacement;
 - Thyroid replacement;

- Obesity medication (6 months prior to screening);
- Omega 3 fatty acids;
- Diabetes medications;

19. Previous intolerance to ezetimibe;

20. A medical or situational (ie, geographical) finding that in the investigator's opinion may compromise the patient's safety or ability to complete the study;

21. An employee or contractor of the facility conducting the study, or a family member of the Principal Investigator, Co-Investigator, or Sponsor.

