10.5.2. Treatment Week 0 (Visit T1; Day 1)

Prior to scheduling Visit T1, screening results will be reviewed to determine whether the patient continues to meet eligibility criteria. At Visit T1, a physical exam, ECG and urine pregnancy test will also be completed prior to randomization. Patients not meeting all entry criteria at any point prior to randomization will be screen failures.

If the patient has met all inclusion criteria and none of the exclusion criteria, the patient may be randomized into the double-blind Treatment Period.

At randomization, patients will be stratified based on baseline/current statin intensity (High vs. Other) and disease characteristics (ASCVD and/or HeFH vs. multiple CV risk factors). High intensity statin includes atorvastatin 40-80 mg/day and rosuvastatin 20-40 mg/day, all others will be categorized as 'other' for randomization and stratification purposes. Definition of ASCVD and/or HeFH or multiple CV risk factors are provided in inclusion criteria.

The patient will undergo the following assessments and procedures:

- Concomitant medication review (ongoing);
- Assess AEs and SAEs;
- PE;
- ECG;
- Urine pregnancy test (in female patients of childbearing potential);
- Review inclusion/exclusion criteria to establish patient eligibility;
- Randomize the patient and obtain MED ID number for double-blind IMP;
- Weight;
- Vital signs;
- Central clinical laboratory evaluations:
 - Hematology, blood chemistry, and urinalysis;
 - Basic fasting lipids (TC, calculated LDL-C, HDL-C, non-HDL-C, and TG);
 - ApoB and hs-CRP;
- Dispense double-blind IMP and provide dosing and storage instructions.

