12.1.6.4.3. Monitoring and Management of Elevated TG

Patients may continue to use stable doses of TG-lowering medications (except fibrates) during the study. Post-randomization, TG results will be masked to investigators in order to maintain the blind; however, a threshold has been set to notify investigators and provide an opportunity to adjust the patient's standard of care regimen. If the TG level exceeds 1000 mg/dL (11.3 mmol/L) while on treatment, the investigator will receive notification from the central laboratory that the patient has met or exceeded the protocol defined threshold criteria for TG.

- Any patient with initial report of TG >1000 mg/dL (11.3 mmol/L), will be counseled on healthy dietary guidelines, and reminded to take IMP and other background medications as directed and fast for at least 10 hours prior to repeat TG assessment.
- Patient will return to clinic within 1 week for a repeat, fasting TG assessment to confirm the TG value meets the threshold criteria.

- Any patient with a confirmed TG >1000 mg/dL (11.3 mmol/L) will have TG lowering medications (except fibrates) adjusted or added if possible to lower TG. Changes in medications will be documented on the case report form. These medications will not be provided by the sponsor.

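### Exclusion criterion 17 and Protocol Section 8.2.2 prohibit different drugs over the same window, so a patient can be eligible for randomization and already in breach on Day 1

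*Protocol*

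**What the plan says.** Criterion 17 in Protocol Section 7.2, repeated in the synopsis, opens with "Use of any of the following drugs within 5 weeks prior to screening (Visit S1) unless otherwise stated or a plan to use these drugs" and goes on to prohibit planned use during the study. Its list has three parts: systemic corticosteroids, simvastatin at or above 40 mg/day, and non-statin LDL-C-modifying therapies.

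Section 8.2.2 sets the same window: "within 5 weeks prior to Visit S1 (unless otherwise stated) or a plan to use these drugs during the study is" prohibited. It repeats the three parts and then adds a further block of other drugs. That block reads "Probenecid or cyclosporine", followed by an entry beginning "Potent CYP3A4 inhibitors including amiodarone, azoles" and continuing through a long list that includes diltiazem and verapamil.

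Section 10.5.2 states the condition for randomization: "If the patient has met all inclusion criteria and none of the exclusion criteria, the patient may be randomized" into the treatment period.

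On triglycerides, Section 12.1.6.4.3 says that a patient with a confirmed value above 1000 mg/dL "will have TG lowering medications (except fibrates) adjusted or added if possible to lower TG".

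**The concern.** Two lists that share a window should share their content. If they do not, a site that screens from Section 7.2 and a site that screens from Section 8.2.2 can reach different decisions on the same patient, and both can point to the protocol.

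Three things are at stake: who may enter, whether the interaction list protects patients from the first dose, and whether deviations are classified in the same way across about 125 sites. The analysis of LDL-C is a lesser matter here.

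**Working it through.** The main point needs no arithmetic, and the documents as given state no power, effect size or SD to reproduce. The texts are set side by side.

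| Item | Section 7.2, criterion 17 (and synopsis) | Section 8.2.2 |
|---|---|---|
| Window | 5 weeks before S1, or planned use on study | Same |
| Corticosteroids, simvastatin, non-statin lipid drugs | Listed | Listed |
| Probenecid, cyclosporine | Not named | Prohibited |
| CYP3A4 inhibitors, including amiodarone, diltiazem, verapamil | Not named | Prohibited |
| Niacin | No dose qualifier | Qualifier of more than 500 mg/day for crystalline over-the-counter niacin |

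**Step 1: does another criterion close the gap?** Criterion 4 excludes arrhythmia medication only if it was started or its dose changed within 3 months of screening, so long-standing stable use passes. No other exclusion criterion names the drugs in the added block.

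**Step 2: is there a second check at randomization?** Section 10.5.2 ties randomization to the inclusion and exclusion criteria. Section 8.2.2 is not part of that condition.

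**Step 3: what happens to such a patient afterwards?** The procedure in Section 10.6.1 is for patients who fail enrollment criteria, and this patient meets them. SAP Section 5.2.3 judges entry violations against the inclusion and exclusion criteria but reviews on-study deviations for prohibited therapies. The same patient on the same drug is compliant at entry and a deviator on study. Section 10.6.3 lists the need for a prohibited drug only as a possible reason to stop study drug.

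**Step 4: niacin wording.** The entry text is the stricter one. A patient who passes criterion 17 on niacin cannot breach Section 8.2.2 through this difference, so it creates no Day 1 violation. It does leave low-dose crystalline niacin on study open to two readings, depending on whether the word introducing the examples in Section 8.2.2 is read as illustrative or limiting.

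**Step 5: scale of the triglyceride rule.** This is a bound. It assumes that a patient adds a drug that shifts percent change in LDL-C by 17 points, the ceiling in Section 4.1 ("extended-release niacin in doses up to 2 g lowers LDL-C by up to 17" percent).

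- Shift in arm mean = k × 17 / n. For k = 1: 17/100 = 0.17 points in an active arm, and 17/50 = 0.34 points in the placebo arm. A shift of about 1 point needs 6 of 100 (1.02) or 3 of 50 (1.02).
- SE of a difference = SD × √(1/n₁ + 1/n₂). The SD is not in the documents; 15 to 30 points is assumed. FDC vs placebo: 15 × 0.1732 = 2.6, up to 30 × 0.1732 = 5.2. FDC vs a component: 15 × 0.1414 = 2.1, up to 30 × 0.1414 = 4.2.
- One patient therefore moves a comparison by between 0.17/4.24 = 0.04 SE and 0.34/2.60 = 0.13 SE.
- Timing: with a repeat test within 7 days, a drug added after the Week 4 or Week 8 result would be in use for 85 − (29 + 7) = 49 or 85 − (57 + 7) = 21 days by Day 85. An effect on the Week 12 value is possible in principle.

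**The case against.** The best defence is that Section 8.2.2 stands on its own. Criterion 17 does not permit the added drugs; it is silent on them. The Schedule of Events has a row for concomitant and prohibited medications marked at S1 and T1, and Sections 10.5.1 and 10.5.2 call for medication review at both visits. Criterion 20 lets the investigator exclude a patient on safety grounds, and Section 10.5.2 allows randomization without requiring it. All of this is correct, and it means a site could enrol such a patient, not that it will. It does not close the gap: a review may detect the drug, but no text makes it a reason for exclusion, and criterion 20 is discretionary.

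A reader might also infer several stronger claims that the documents do not support.

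- *That the protocol contradicts itself in three places.* The first difference is an omission from the entry criteria, the second turns on one word, and the third is an incomplete exception.
- *That the triglyceride rule brings a prohibited LDL-C-lowering drug into the primary endpoint.* The rule neither names niacin nor lifts Section 8.2.2, and the documents never describe niacin as triglyceride-lowering. The rule also needs a confirmed value above 1000 mg/dL in a patient who entered below 500 mg/dL. It is fair to say that naming only fibrates, which Section 8.2.2 already bars, invites misreading.
- *That each affected patient carries a shift the size of a component's effect,* because 17% is close to the 18% cited for ezetimibe. This compares one patient's value with a group effect.
- *That violators drop out of the analysis.* The full analysis set keeps every randomized patient. For protocol deviations, removal from the PK set applies only to major ones found to have affected the PK data.

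**Conclusion.** The point holds in its narrow form: the entry criteria and Section 8.2.2 do not list the same prohibited drugs over the same window, and an eligible patient can be in breach from screening onward. This should be corrected because it bears on who may enter, on patient safety and on consistent handling of deviations.

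The number of patients affected is unknown, since the documents do not give the share taking the listed drugs; each 1% of the planned 350 would be 3.5 patients. The niacin and triglyceride points are secondary wording matters. No material effect on the co-primary comparisons is shown: about 0.04 to 0.13 SE per affected patient, under the assumed SD of 15 to 30 points and the cited 17% ceiling. The conclusion takes no position on which drugs ought to be prohibited.

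**What to change.** Reconcile criterion 17 in Section 7.2, its copy in the synopsis, Section 8.2.2 and Section 12.1.6.4.3, so that one list with one set of limits governs both entry and on-study use. Have the triglyceride rule refer to that list in place of its own partial exception. The sponsor's medical team decides which drugs and limits the list contains.

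The cost is a wording amendment to three sections and the synopsis. It needs no additional patients, visits or data.

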8.2.3. Permitted Medications

Patients in this study may be using a wide range of concomitant medications, according to local standard of care for their medical conditions. Permitted medications must be stable for at least 2 weeks prior to Visit S1 (Week -2) with the exception of the medications described below.

The following permitted medications that may impact plasma lipid levels are allowed provided that they are stable at least 5 weeks prior to screening (Visit S1) unless otherwise noted:

- Hormone replacement;
- Thyroid replacement;
- Obesity medication (6 months prior to screening);
- Omega 3 fatty acids;
- Diabetes medications.

8.3. Treatment Assignment, Randomization, and Blinding

During the Treatment Period, patients will receive double-blind IMP. At Day 1 (Visit T1), patients will be randomized to receive either BA 180 mg + EZE 10 mg FDC, BA 180 mg, EZE 10 mg or placebo. The randomization will be stratified by baseline statin intensity (high intensity vs. other) and disease characteristics (ASCVD and/or HeFH vs. multiple CV risk factors). Only atorvastatin 40-80 mg/day and rosuvastatin 20-40 mg/day are considered high intensity statin and all others will be considered as ‘other’ for randomization purpose. The criteria for determining these 2 stratification factors are further detailed in [Section 7.1](#)). The investigator or designee will utilize Interactive Web Response System (IWRS) during the visit to randomize the patient and obtain the appropriate IMP container via medication identification numbers (MED ID). A patient is considered to be randomized when the corresponding randomization box is checked within the eCRF.

Randomization will be determined by a computer-generated random code and will correspond to a treatment group according to patient’s sequential entrance into the study. The randomization schedule for blinding of treatment assignment will be generated by the contract research organization (CRO), provided to IWRS, and released only after the study is complete and the database is locked.

During the Treatment Period, Sponsor, site personnel, CRO, and patient will all be unaware of patient’s treatment assignment; an independent bio-analytical lab will be aware of treatment assignment only to support PK sample analysis.

Blinding of treatment must be maintained for all patients unless, in the opinion of the investigator, the safety of the patient may be at risk. Only under the rarest of circumstances should the investigator consider breaking the blind and only when medical/supportive care cannot be provided without determining if the patient is receiving active drug treatment. In the event that the blind needs to be broken prior to completion of the study, the investigator should contact the appropriate Medical Monitor by telephone. If the blind must be broken prior to

consultation with the Medical Monitor, contact must be made within 24 hours of breaking the blind.

At the initiation of the study, the clinical site will be instructed on procedures for breaking the blind via the IWRS. In all cases of breaking the blind, the investigator must document in the patient's medical record the date, time, and reason for breaking the blind, and the names of personnel involved.

Post-randomization values for individual laboratory measures for LDL-C, non-HDL-C, TC, ApoB, hs-CRP, TG and HDL-C that may inadvertently suggest treatment assignment will not be available to personnel from the clinical site, the patient, the Sponsor, or the CRO. While knowledge of these values does not truly 'unblind,' the collection of these lab assessments by the investigator, all collaborating physicians, or the patients locally (outside the study visits) is strongly discouraged. Investigators should not perform testing of these analytes at the local lab during the conduct of the study.

9. INVESTIGATIONAL MEDICINAL PRODUCT

9.1. Description of Investigational Medicinal Product

Table 2: Investigational Medicinal Products

Product Name:	Investigational Medicinal Product	
	Bempedoic acid	Placebo to Match Bempedoic Acid
Dosage Form:	Film-coated tablets	Film-coated tablets
Unit Dose:	180 mg	Not applicable
Container/Closure:	9 count blister card with child resistant closures	9 count blister card with child resistant closures
Route of Administration:	Oral, daily at approximately the same time, with or without food	Oral, daily at approximately the same time, with or without food
Physical Description:		
Product Name:	Investigational Medicinal Product	
	Ezetimibe	Placebo to Match Ezetimibe
Dosage Form:	Over-encapsulated tablets	Capsules
Unit Dose:	10 mg	Not applicable
Container/Closure:	9-count blister card with child-resistant closures	9-count blister card with child-resistant closures
Route of Administration:	Oral, daily at approximately the same time, with or without food	Oral, daily at approximately the same time, with or without food
Physical Description:		
Product Name:	Investigational Medicinal Product	
	Bempedoic acid + ezetimibe FDC	Placebo to Match Bempedoic acid + ezetimibe FDC
Dosage Form:	Tablets	Tablets
Unit Dose:	180 mg/10 mg	Not applicable
Container/Closure:	9-count blister card with child-resistant closures	9-count blister card with child-resistant closures
Route of Administration:	Oral, daily at approximately the same time, with or without food	Oral, daily at approximately the same time, with or without food
Physical Description:		

Please see Pharmacy Manual for detailed storage requirements and instructions and additional information.

9.2. Investigational Medicinal Product Supply and Control

The Sponsor will supply the IMP for this study as described above. IMP will be distributed and released in accordance with regional and local requirements during the conduct of the study.

The MED ID number (an identifier on the IMP packaging) will be obtained via IWRS and used to select double-blind IMP from available clinical supplies at the clinical site.

IMP will be dispensed by the investigator or other qualified site personnel only to appropriate patients who have provided written informed consent.

9.3. Packaging and Labeling

Double-blind IMP will be packaged in blister packs. Each blister pack will contain a 9-day supply and 4 blister packs will be provided in the drug kit.

The IMP labels will include protocol number, MED ID number, patient identification number, lot number, site number and investigator name in addition to standard language regarding warnings and regulations, administration and storage of the product.

9.4. Investigational Medicinal Product Adherence

At each clinic visit during the Treatment Period, designated clinical site staff will assess patient IMP intake adherence by counting the number of tablets that are returned as unused and by querying the patient with regards to daily intake. If the patient has not taken multiple doses as instructed, the patient will be queried for a reason, findings will be documented, and the patient will be counseled on the importance of carefully following all dosing instructions. Factors contributing to poor adherence will be determined and, if possible, remedied. Patients demonstrating poor adherence during the Treatment Period will continue to be counseled on the importance of carefully following all dosing instructions, but will not be removed from the study.

9.5. Investigational Medicinal Product Accountability

Patients will be instructed to return all packaging and unused IMP at every visit for assessment of adherence and drug accountability.

Accurate records of the receipt of all IMP shipped by the Sponsor (or designee) and the disposition of that IMP must be maintained.

IMP records or logs must comply with applicable regulations, local law, and guidelines, and should include:

- Amount received/placed in storage area;
- Amount currently in storage area;
- MED ID number for all IMP;
- Dates and initials of person(s) responsible for IMP inventory (including entry/movement/disposition);
- Date and amount of IMP dispensed to each patient, including unique patient identifiers;
- Date that IMP was returned by patient, assessment of adherence, and relevant documentation of discrepancies;

- Nonstudy disposition (e.g., lost, broken, wasted);
- Amount returned to Sponsor (or designee)/destroyed or amount destroyed per local standard operating procedure (SOP) following accountability by site monitor.

